## 7 URGENT SAFETY MEASURES

An urgent safety measure is an immediate action taken, which is not defined by the protocol, in order to protect subjects participating in a clinical trial from immediate harm, these do not constitute de facto deviation from the protocol. Urgent safety measures may be taken by the Sponsor (or a nominated designee) or clinical Investigator, and may include any of the following:

- Immediate change in study design or study procedures
- Temporary or permanent halt of a given clinical trial or trials
- Any other immediate action taken in order to protect clinical trial participants from immediate hazard to their health and safety

The Investigator may implement urgent safety measures to protect study subjects from immediate hazard to their health or safety. The measures should implement immediately and does not require prior authorization from the Sponsor (or a nominated designee). In the event(s) of an apparent direct hazard to the subject, the Investigator will notify the Sponsor (or a nominated designee) immediately by phone and confirm notification to the Sponsor (or a nominated designee) in writing as soon as possible, and within 1 calendar day after the change is implemented. The Sponsor (or a nominated designee) will also ensure the responsible EC(s) and relevant competent authority(s) are notified of the urgent safety measures taken in such cases according to local regulations.

## **8 REGULATORY AGENCY, INSTITUTIONAL REVIEW BOARD, ETHICS COMMITTEE, AND SITE REPORTING**

The Sponsor (or a nominated designee) and CRO are responsible for notifying the relevant regulatory authorities/US local IRB of related, unexpected SAEs.

In addition, the Sponsor (or a nominated designee) is responsible for notifying active sites of all related, unexpected SAEs occurring during all interventional studies across the asapiprant program.

The Investigator is responsible for notifying the local IRB/EC of SAEs or significant safety findings, or the relevant local regulatory authority of all SAEs that occur at his or her site as required by IRB/EC procedures.

## **APPENDIX 4**

## CHILD-PUGH SYSTEM

	Points Scored for Observed Findings		
	1	2	3
Encephalopathy grade 	none	1 or 2	3 or 4
Ascites	absent	slight	moderate
Serum bilirubin, mg/dL	< 2	2 to 3	> 3
Serum albumin, g/dL	> 3.5	2.8 to 3.5	< 2.8
Prothrombin time, sec prolonged	< 4	4 to 6	> 6

 Assessment as good operative risk (A or mild) if 5 or 6 points; moderate risk (B or moderate) if 7 to 9 points; and poor operative risk (C or severe) if 10 to 15 points. (Developed for surgical evaluation of alcoholic cirrhotic.)

 Grade 0: normal consciousness, personality, neurological examination, electroencephalogram  
Grade 1: restless, sleep disturbed, irritable/agitated, tremor, impaired handwriting, 5 cps waves  
Grade 2: lethargic, time-disoriented, inappropriate, asterixis, ataxia, slow triphasic waves  
Grade 3: somnolent, stuporous, place-disoriented, hyperactive reflexes, rigidity, slower waves  
Grade 4: unrousable coma, no personality/behavior, decerebrate, slow 2-3 cps delta activity

4.0	14MAR2022	[REDACTED]	Updated per FDA comments dated November 24, 2021 and BioAge response.
5.0	01JUN2022	[REDACTED]	
1. Update on primary endpoint analysis by removing baseline WHO ordinal scale/ Addendum is added for the justification.2. Other minor corrections

1 Introduction

This Statistical Analysis Plan (SAP) contains a more technical and detailed elaboration of the principal features of the analysis described in the protocol and includes detailed procedures for executing the statistical analysis. This SAP should be used in conjunction with the protocol. If there are any discrepancies between the protocol and SAP, this SAP will prevail. Any deviations from this SAP that are implemented in the final analysis will be documented with sound clinical and statistical rationale in the Clinical Study Report (CSR). In the event of any changes to the primary endpoints or analyses, these changes will be documented through a protocol amendment, consistent with ICH E9 Statistical Principles for Clinical Trials.

The SAP is based on protocol v5.0, Amendment 04 dated 07 Sep 2021.

Pharmacokinetics (PK) and pharmacodynamics (PD) analyses and reporting are not included in this analysis plan.

A separate document contains the table, figure and listing specifications and any example programming codes.

2 Study Design

This is a randomized, placebo-controlled, parallel-group, multicenter, double-blind study of asapiprant (BGE-175) administered by oral administration (PO) or through a nasogastric tube (NG) in patients \geq 50 years of age and hospitalized with documented coronavirus disease 2019 (COVID-19) infection who are not yet in respiratory failure (RF).

After signing informed consent, patients will be screened upon presentation at the hospital. Screening will include full physical examination, vital signs, safety laboratory evaluation, oxygen (O_2) saturation, pre-diagnostics to measure prostaglandin D2 (PGD2) status, and baseline assessment of World Health Organization (WHO) Ordinal Scale for COVID-19 that is derived from O_2 supplementation requirements. If confirmed that they qualify for this protocol according to listed inclusion and exclusion criteria, patients will receive their first dose of investigational medicinal product (IMP). They will then receive IMP PO or NG (if intubated or unable to swallow medication) once daily, at approximately the same time each day for up to 13 additional days. IMP will be administered in addition to standard of care deemed appropriate by the treating physician(s). Patients will be randomized to receive asapiprant or placebo in a blinded manner. Patients will be monitored daily for all relevant efficacy outcomes, O_2 saturation and adverse events (AEs). Blood will be drawn periodically for safety laboratory measurements, plasma kinetics, lymphocyte subsets, CRP, and cytokines (see protocol, Table 1 Schedule of Assessments). Nasopharyngeal swabs will be collected to measure viral load. Patients will be monitored at follow-up visits on Day 28 (approximately 14 days after the last dose) and Day 57 (approximately 43 days after last dose).

Treatment Period

Each patient will participate in the study for approximately 8 weeks from the time the patient signs the informed consent form (ICF) through the final contact. After screening, each patient will receive, daily, 1 dose of assigned treatment between Day 1 and Day 14. The WHO Ordinal Scale for COVID-19 will be derived daily while hospitalized, at Day 14, and at follow-up visits until the patient has completed the study.

2.1 The Study Objectives

Primary Objective

QMS Document Name: Statistical Analysis Plan	Page 8 of 27
QMS No (include version ref): STF-015-GL.02	Document date: 09JUL2019
CONFIDENTIAL	

- To evaluate the efficacy of asapirant given by PO or NG administration versus placebo on the clinical signs and symptoms of COVID-19 infection in hospitalized patients ≥ 50 years of age.

Secondary Objectives

- To evaluate the ability of asapirant given by PO or NG administration to accelerate the clearance of the COVID-19 virus in patients with symptomatic disease requiring hospitalization.
- To determine the efficacy of asapirant by demonstrating improvement in COVID-19 illness and prevention of progression to RF using various endpoints.
- To evaluate the safety profile of asapirant given by PO or NG administration in patients ≥ 50 years of age hospitalized with COVID-19 infection.

Other Objectives

- To investigate the effect of asapirant on inflammation markers of COVID-19 infection, including but not limited to interleukin (IL)-6, C-reactive protein (CRP), IL-10, tumor necrosis factor alpha (TNF- α), interferon gamma (IFN- γ), interferon alpha (IFN- α), IFN- γ -induced protein 10 (IP-10), monocyte chemoattractant protein-1 (MCP-1), cluster of differentiation (CD)4+ and CD8+ T cells, and absolute lymphocyte count.
- Determine peak and trough concentrations of study drug after first dose and at steady state and, if possible, develop a population PK model.

2.2 Sample Size Determination

The sample size estimate of 312 total subjects is based on 31% progressing to RF by Day 28 in the placebo group and 15% progressing to RF in the asapirant group using data from recently published COVID-19 studies (Guimaraes et al 2021, Temesgen et al, 2021). Using a Fishers Exact test with two-sided 5% Type 1 error and 90% power, the sample size to detect a 16% absolute improvement in the primary endpoint is 312 patients (1:1 randomization). Randomization will be stratified based on the patient's enrollment region (North America vs. South America) and age (50 to < 75 vs. ≥ 75 years of age).

2.3 Study Endpoints and Evaluations

Primary Endpoint

- Proportion of patients who have died or progressed to RF as defined by progressing to the need for high-flow nasal cannula O₂ delivery, noninvasive positive pressure ventilation, invasive mechanical ventilation, or extracorporeal membrane oxygenation (ECMO) therapy by Day 28.

Secondary Endpoints

1. Safety as assessed by AEs as measured by the Common Terminology Criteria for Adverse Events (CTCAE) v 5.0
2. Proportion of patients surviving [Time Frame: at Day 14, at Day 28, at Day 57]
3. Proportion of subjects who survive without progression to RF [Time Frame: at Day 14, at Day 28, at Day 57]

QMS Document Name: Statistical Analysis Plan	Page 9 of 27
QMS No (include version ref): STF-015-GL.02	Document date: 09JUL2019
CONFIDENTIAL	

4. Time to two successive negative viral titers in nasopharyngeal swab
5. Time to clinical worsening from baseline value (defined by time to ≥ 1 -point worsening on WHO Ordinal Scale for COVID-19):

World Health Organization Ordinal Scale for COVID-19

Patient State	Description	Score
Uninfected	No clinical or virological evidence of infection	0
Ambulatory	No limitation of activities	1
	Limitation of activities	2
Hospitalized, Mild Disease	Hospitalized, no oxygen therapy	3
	Oxygen by mask or nasal prongs	4
Hospitalized, Severe Disease	Noninvasive ventilation or high-flow oxygen	5
	Intubation and mechanical ventilation	6
	Ventilation + additional organ support – pressors, RRT, ECMO	7
Dead	Death	8

Abbreviations: ECMO = extracorporeal membrane oxygenation; RRT = renal replacement therapy

6. Proportion of patients who develop critical COVID-19 illness as defined by at least one the following:
 - A. Respiratory failure defined based on resource utilization requiring at least one of the following: Endotracheal intubation and mechanical ventilation, oxygen delivered by high-flow nasal cannula (heated, humidified, oxygen delivered via reinforced nasal cannula at flow rates > 20 L/min with fraction of delivered oxygen ≥ 0.5), noninvasive positive pressure ventilation, ECMO clinical diagnosis respiratory failure (i.e., clinical need for one of the preceding therapies, but preceding therapies not able to be administered in setting of resource limitation)
 - B. Hemodynamic compromise (defined by systolic blood pressure < 90 mm Hg, or diastolic blood pressure < 60 mm Hg or requiring vasopressors)
 - C. Multi-organ dysfunction/failure
7. Time to clinical improvement from baseline value (defined by time to ≥ 1 -point improvement on WHO Ordinal Scale for COVID-19 score – must be maintained through Day 28)
8. Mean change from baseline in WHO Ordinal Scale for COVID-19 score at Day 14/End of Treatment, Day 28, Day 57
9. Incidence and duration of intubation
10. Length of intensive care unit stay (ICU)
11. Incidence and duration of supplemental O₂ administration
12. Incidence and duration of noninvasive ventilation or high-flow nasal cannula O₂ administration

13. Incidence and duration of mechanical ventilation
14. Incidence and duration of mechanical ventilation plus additional organ support using vasopressors, and/or renal replacement therapy and/or ECMO
15. Daily ratio of oxygen saturation (SpO_2) to fractional inspired O_2 ($\text{SpO}_2/\text{FiO}_2$)
16. Length of hospital stay
17. Incidence of re-hospitalization through Day 57
18. Proportion of patients requiring intensive care unit admission post randomization

Exploratory Endpoints

1. Inflammation markers including: IL-6, CRP, IL-10, TNF- α , IFN- γ , IFN- α , IP-10, MCP-1, and absolute lymphocyte count
2. Assess peak and trough concentrations of asapiprant at steady state
3. Assess PGD2 pre-diagnostic to assess correlation with response to treatment for COVID-19 based on change in the WHO Ordinal Scale for COVID-19 score

Safety endpoints

1. Incidence and severity of treatment-emergent AEs (TEAEs)
2. Safety outcome measure:
 - a. Occurrence of AEs
 - b. Laboratory safety parameters such as complete blood count, blood glucose, electrolyte, hepatic and renal functions taken before the first dose and on Days 2, 5, 14 and 28 and the time of discharge to find any changes or any systemic effect after treatment

3 Analysis Sets

Enrolled Analysis Set: all patients who provided informed consent.

Intent-to-Treat (ITT): all patients who have been randomized. The ITT will be used for efficacy endpoints. Patients will be analyzed according to the treatment group to which they were randomized. The ITT will be used for the primary efficacy analysis.

Modified Intent-to-Treat population (mITT): all ITT patients with exclusion of randomized untreated patients and randomized ineligible patients.

Per-protocol Set (PPS): all mITT patients with further exclusion of patients with major protocol deviations related to data integrity or eligibility as judged by clinical/biostatistical study personnel prior to database lock. This population will be formed only if > 5% of patients would be excluded.

Safety Analysis Set (SAF): all patients who have received at least 1 dose of either asapiprant or placebo. The SAF will be used for safety analysis. Patients will be analyzed under actual treatment being received.

Pharmacokinetic (PK) Set: all patients who have received at least 1 dose of asapiprant and have at least 1 evaluable post-dose PK concentration value.

Pharmacodynamic (PD) Set: all patients who have received at least 1 dose of asapiprant and have at least 1 evaluable post-dose PD value.

QMS Document Name: Statistical Analysis Plan	Page 11 of 27
QMS No (include version ref): STF-015-GL.02	Document date: 09JUL2019
CONFIDENTIAL	

The assignment of patients to the different analysis set will be done prior to unblinding during a blind data review meeting. All patients excluded from the different analysis sets will be listed together with the reason for exclusion.

The table below displays how different analyses will be applied to the different analysis sets:

Analysis	Enrolled	mITT	ITT	PPS	SAF	PK	PD
Disposition	X						
Protocol Deviation			X				
Exposure and compliance					X		
Demography and baseline characteristics			X				
Medication History			X				
Primary efficacy		X	X	X			
Secondary efficacy		X	X	X			
Safety						X	
PK							X
PD							X

4 General Consideration for Data Analysis

All analyses will be conducted using SAS® version 9.3 or later (SAS Institute, Cary, NC 27513).

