### **2.3.3 Exploratory Endpoints**

1. Inflammation markers including: IL-6, CRP, IL-10, TNF- $\alpha$ , IFN- $\gamma$ , IFN- $\alpha$ , IP-10, MCP-1, CD4+ and CD8+ T cells, and absolute lymphocyte count
2. Assess peak and trough concentrations of asapiprant at steady state
3. Assess PGD2 pre-diagnostic to assess correlation with response to treatment for COVID-19 based on change in WHO Ordinal Scale for COVID-19 score

[figure not shown]

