### **7.2.7 Pre-dose Serological Markers - PGD2**

A single predose blood sample for circulating PGD2/PGD2 metabolites will be obtained at the time specified in [Table 1](#). Sample collection, handling, storage and shipment instructions will be provided in the study laboratory manual.

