4.3 Subgroups

The following sub-groups will be examined for the primary endpoint. Results will be displayed in both tabular form. Subgroup analyses are exploratory.

- Age (50 to < 75 vs \geq 75)
- Gender (male vs female)
- previous COVID-19 therapy (yes vs no)
- Regions (North America vs South America)
- Baseline WHO ordinal clinical scale (3 or 4)

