The following demographic characteristics will be summarized by treatment group and overall for patients in ITT population using descriptive statistics. No statistical hypothesis tests will be performed.

- Sex (male, female)
- Age (years)
- Age group (50 to < 75, ≥ 75 years)
- Race (American Indian or Alaska Native, Asian, Black or African American, Native Hawaiian or other Pacific Islander, White, Unknown, Other)
- Ethnicity (Hispanic or Latino, not Hispanic or Latino, not reported, unknown)
- Weight (kg) at baseline
- Height (cm) at baseline

QMS Document Name: Statistical Analysis Plan	Page 16 of 27
QMS No (include version ref): STF-015-GL.02	Document date: 09JUL2019
CONFIDENTIAL	

- BMI (kg/m²) at baseline
- SARS-CoV-2 (COVID-19) history
- PGD2 result at baseline
- Virus serology result of presence of HIV, Hepatitis B surface antigen (HBsAg), and HCV antibody if collected in eCRF.

Demographics and other baseline characteristics will be provided in a data listing by patient.

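### The exploratory PGD2 endpoint is framed as a correlation with outcome, and no planned analysis tests whether the asapiprant-placebo difference varies with PGD2

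*SAP*

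**What the plan says.** The SAP (2.3, exploratory endpoint 3) states the endpoint as "Assess PGD2 pre-diagnostic to assess correlation with response to treatment for COVID-19", judged by change in the WHO score. Protocol 2.3.3 and the synopsis say the same in nearly identical words. None of these places gives an arm, time point, coefficient or model.

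The marker is measured once: "A single predose blood sample for circulating PGD2/PGD2 metabolites will be obtained" (Protocol 7.2.7). Table 1 of the protocol schedules the sample on Day 1 without restricting it to one arm.

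The only SAP output that uses the marker is in section 6.1, where "PGD2 result at baseline" is one item in the baseline table by treatment group. Of that table the SAP says "No statistical hypothesis tests will be performed". PGD2 is absent from the covariates (4.2), from the list introduced by "The following sub-groups will be examined for the primary endpoint" (4.3), from the efficacy analyses (10) and from the inflammation-marker summaries (12). Protocol 8.9 plans no further analyses.

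**The concern.** Calling PGD2 a pre-diagnostic for treatment response raises a predictive question: is the benefit of asapiprant over placebo larger at some PGD2 levels than at others? One subject's change in WHO score is not a measure of drug benefit, because subjects also recover or deteriorate on placebo plus standard of care. A correlation between baseline PGD2 and that change, in treated subjects or in everyone, mixes prognosis with effect modification.

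Prognosis is a live explanation in this trial. Protocol 1.2.2 states that suppression of the antiviral response through this pathway goes with worse outcome. The SAP addendum reports, from blinded data, that no subject with a baseline WHO score of 3 had respiratory failure, so a baseline variable can be strongly prognostic here whatever the assigned arm. If PGD2 tracks baseline severity, it would correlate with outcome even if it said nothing about who benefits. The opposite error is also possible: a truly predictive marker can show no correlation among treated subjects. At stake is what the trial can say about a marker on the drug's own target pathway. The primary result is not affected.

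**Working it through.** **1. The plan's own figure.** No figure is given for the PGD2 endpoint. The trial size (SAP 2.2: 31% vs 15%, two-sided 5%, 90% power, Fisher's exact test, 1:1) reproduces. The continuity-corrected formula gives 156 per arm, 312 in total. Exact enumeration at 156 per arm gives power 0.905. So 156 per arm is a fair planning number. The SAP addendum says that enrolment stopped before the interim analysis, which was planned at about 208 patients, and the final N is not given. I therefore also use 104 per arm as an illustration.

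**2. How often a prognostic-only marker gives a significant treated-arm correlation.** The r values are assumptions. With Fisher's z, power ≈ Φ(√(n−3) × atanh(r) − 1.96).

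| n in asapiprant arm | r | √(n−3) × atanh(r) | Power |
|---|---|---|---|
| 156 | 0.2 | 12.369 × 0.2027 = 2.507 | Φ(0.547) = 0.708 |
| 156 | 0.3 | 12.369 × 0.3095 = 3.828 | Φ(1.868) = 0.969 |
| 104 | 0.2 | 10.050 × 0.2027 = 2.037 | Φ(0.077) = 0.531 |
| 104 | 0.3 | 10.050 × 0.3095 = 3.110 | Φ(1.150) = 0.875 |

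A simulation of 3,000 trials at N=312 gave 0.707 and 0.970 for the treated-arm correlation at r=0.2 and 0.3. The treatment-by-marker interaction test was significant in 0.051 and 0.055, its nominal rate.

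**3. The same correlation under different truths.** For simple arithmetic, use death or respiratory failure as a binary outcome, and split the marker into equal low and high halves. In every scenario the arm averages are the plan's 31% and 15%; the split by marker is assumed. Within an arm, φ = (high − low) × 0.5 / √(p(1−p)), with p the average. For asapiprant at 23%/7%, that is −0.16 × 0.5 / √(0.15 × 0.85) = −0.224.

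| Scenario | Placebo low/high | Asapiprant low/high | φ asapiprant | φ pooled | Benefit low/high (points) |
|---|---|---|---|---|---|
| A, prognostic only | 39%/23% | 23%/7% | −0.22 | −0.19 | 16/16 |
| B, predictive only | 31%/31% | 23%/7% | −0.22 | −0.10 | 8/24 |
| C, predictive with opposing prognosis | 23%/39% | 15%/15% | 0.00 | +0.10 | 8/24 |

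Benefit is on the risk-difference scale. A and B have the same treated-arm correlation but different benefit patterns. B and C have the same benefit pattern but different correlations, and their pooled correlations have opposite signs.

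**4. Continuous version.** I simulated 4,000 trials at N=312 with a normal marker, a normal outcome and assumed slopes of 0.3 SD.

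| Scenario | Mean r, asapiprant | Mean r, placebo | Treated-arm r significant | Interaction significant |
|---|---|---|---|---|
| Prognostic only | −0.29 | −0.29 | 96% | 4% |
| Predictive only | −0.29 | 0.00 | 95% | 74% |
| Predictive with opposing prognosis | 0.00 | 0.29 | 6% | 74% |

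**5. What the interaction test could deliver.** Take scenario B. The interaction is 24 − 8 = 16 points. Its variance is (0.31×0.69 + 0.31×0.69 + 0.23×0.77 + 0.07×0.93)/m = 0.67/m, with m subjects per arm-by-marker cell. At N=312, m=78, SE = 0.0927 and power = Φ(0.16/0.0927 − 1.96) = 0.41. At N=208, m=52, SE = 0.1135 and power = 0.29. At N=624, the cap for sample-size increase, power is 0.69.

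**The case against.** The strongest reply is that the plan never specifies the analysis criticised in the working. No text confines the correlation to the 156 planned asapiprant subjects. SAP 4.1 says that results are shown by treatment group, with asapiprant, placebo and total columns. Shown that way, a purely prognostic marker would be expected to have similar correlations in both arms, and a careful reader could see it. This stands as a limit on the point: the treated-arm figures are an illustration, not a prediction of what will be reported. It does not remove the gap. Two correlations side by side are not a comparison of them, and no such comparison is planned.

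A second reply is that SAP section 1 places pharmacodynamic analyses outside this plan, so a PGD2 analysis might be described elsewhere. That is possible, but neither document points to one for this endpoint. The SAP's pharmacodynamic set contains asapiprant subjects only, so an analysis restricted to it would have no placebo comparison.

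A third reply is that the endpoint is exploratory, with no cut-off, decision rule or claim attached, and that an interaction test would be weak. Both statements are true. They lower the importance of the point and mean that the remedy is an estimate with its interval, not a test to be passed.

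A reader might infer that the trial will label a prognostic marker as predictive, or that this analysis will select patients for the next trial. The documents support neither. They state no interpretation rule, and apart from the term pre-diagnostic nothing ties PGD2 to patient selection.

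**Conclusion.** The point holds as a minor one. The only stated approach to the PGD2 endpoint is an unspecified correlation with WHO-score change. Nothing planned addresses whether the treatment difference varies with PGD2, although the pre-dose sample is scheduled without restriction by arm. A treated-arm or pooled correlation cannot answer that question, whatever its size.

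Under the assumed r of 0.2 to 0.3 for a prognostic-only marker, a treated-arm correlation is significant in about 71% to 97% of trials at 156 per arm and about 53% to 88% at 104 per arm, against about 5% for the interaction test. These figures rest on assumed correlations, and at 104 per arm on an assumed sample size. The marker split, the slopes and the marker-specific event rates in the other illustrations are also assumptions. The logical point needs none of them. Primary, secondary and safety conclusions are unaffected.

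**What to change.** Add one analysis to SAP 12 in place of the unspecified correlation.

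- **Population:** all randomized subjects, both arms, with a baseline PGD2 value.
- **Outcome:** WHO-score change at the SAP's own time points, Days 14, 28 and 57. Carry deaths forward as in SAP 4.4. That rule runs only to Day 28, so state how deaths are handled at Day 57.
- **Model:** the ANCOVA of SAP 10.2.3 with treatment, age group and region, adding baseline WHO score, continuous PGD2 (log-transformed if skewed) and treatment × PGD2.
- **Report:** the interaction estimate with 95% CI and the treatment effect across PGD2 levels, labelled exploratory.
- **Assay details:** name the analyte, since the sample covers PGD2 and its metabolites, and give a rule for values below the limit of quantification.

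The cost is SAP wording and one model at three time points, on data already scheduled for collection. If written before unblinding, it also removes the freedom to choose arm, day and coefficient afterwards. The downside is low precision (about 41% power at N=312 and 29% at N=208 in the 8- versus 24-point scenario), so the result supports estimation only. A non-significant interaction should not be read as evidence that PGD2 is not predictive.
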